The PI ([name]), assisted by the project manager, will be responsible for maintaining communication between the DSMB and the individual project staff. The DSMB will be responsible for monitoring the trial and making decisions about the termination of individual study arms or the study itself. The DSMB will review and approve the research protocol. They will also assess the progress of the trial, including the assessment of data quality, participant recruitment, accrual and retention, participant risk versus benefit, and study outcomes. Corresponding recommendations will be issued at all subsequent meetings. These recommendations will be based on the results and discussion of interim analyses, conducted at one-half, and three-fourths of the target same size. DSMB recommendations may be guided by statistical monitoring guidelines. The DSMB may recommend permanent suspension of enrollment, or temporary suspension pending protocol modification. Following each meeting, and the provision of recommendations and the response from the research team, the Principal Investigator and Project Manager will prepare progress reports to be submitted to the University of Pennsylvania Institutional Review Board and any other IRBs participating in the trial. Prior to submission to these IRBs, the progress reports will be approved by the DSMB chair.

c. Stopping Rules

The PI, in consultation with Co-Investigator and Faculty Statistician [name], has identified TWO trial stopping rules. The DSMB approved these stopping rules as grounds to terminate the trial:

- 1. Early evidence of undue inducement that distorts voluntary informed consent. To detect whether incentives represent undue inducement, the research team will test the statistical interaction between incentive size and risk perception on the outcome of enrollment in the parent RCT. A statistically significant interaction, in the direction that risk perception is less strongly associated with enrollment in higher-payment arms, would be grounds for terminating the trial or suspending a trial arm.

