the outcome of enrollment in the parent trials. We will test two interactions, each in a separate model to avoid collinearity, to determine if incentives represent unjust inducements: that between incentive size and the primary covariate of annual household income, and that between incentive size and the primary covariate of economic well-being. All analyses will be stratified by parent study.

Analyses of interaction terms will be structured as tests of non-inferiority. The null hypothesis, for both trials, will be that the use of incentives meets criteria for undue or unjust inducement. We can reject the null, and conclude the absence of undue or unjust inducement, if the interaction terms are "small" according to pre-specified criteria (in technical terms, the inferiority margin). Said a different way, our analyses are designed to determine if we can exclude the possibility that incentives represent undue or unjust inducements if the resulting interaction terms are sufficiently small. Specifically, we will use one-sided alpha levels of 0.05 to exclude, with 95% confidence, the possibility that any of these interaction odds ratios are >2.0.

We will explore temporal trends in incentives' effects over the study period using stratified analyses. If temporal trends are noted, as may occur if prospective patients learn of the incentives used in these studies, we will adjust for their influence by entering time as a covariate, modeled as a spline. We will evaluate potential effect modifiers (variables in Table 1) using stratified analyses. If differences among strata appear, we will formally test their corresponding interactions with the incentive amount.

TABLE 1 FACTORS FOR ADJUSTMENT AND EXPLORATION OF EFFECT MODIFICATION

Potential factors for adjustment			
Patient level covariates	Variable coding or definition		
• Age	Continuous		
• Gender	Binary		
• Race	Categorical		
Marital status	Categorical		
Education	Categorical		
Income	Categorical		
Economic well-being	Categorical		
Prior research participation	Categorical		
Attitudes towards research:	Continuous, measured using the Research Attitudes Questionnaire-7 (RAQ- 7).		

6. Secondary analysis

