Trial stopping rules were approved by the Data Safety and Monitoring Board for the following events:

a. Undue inducement

To detect if incentives represent undue inducement that could distort voluntary informed consent, the research team will test the statistical interaction between incentive size and risk perception on the outcome of enrollment in the parent RCT.

b. Unjust inducement

To assess the presence of unjust inducement, or preferential participation among participants with either (a) lower income, or (b) reduced financial well-being, two interaction terms will be evaluated in separate models to avoid collinearity. Unjust inducement will be defined as a statistically significant interaction between (a) incentive size and annual household income, or (b) between incentive size and economic well-being, each on the outcome of trial enrollment. One or both of these interactions, if statistically significant in the direction that lower-income persons or persons with reduced economic well-being are more strongly motivated to participate by increasingly large payments, will be considered grounds for terminating the trial or suspending a trial arm.

10. Timing of analysis and adjustment of significance level

Interim analyses will be conducted after 50% and 75% of the data have accrued within each the BASC and MOVE IT trials. In contrast to the final analyses, which will be structured as tests of non-inferiority, the interim analyses will be conducted as superiority tests of the interactions, such that rejection of the null hypothesis indicates evidence of the presence of an interaction between incentive size and one of our three primary covariates. We will use 1-sided significance levels of 0.0055, and 0.0219.

11. Personnel

Interim analyses will be performed by the trial's primary statistician who will conduct all analyses blinded to trial arm. Investigators, the project manager, and the DSMB will remain blinded to treatment arm through completion of analyses. The data manager and faculty statistician have been unblinded as was necessary to perform essential functions of their roles.

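### Final SAP 5.c would report absence of inducement for a final interval lying wholly between OR 1 and OR 2.0, although 9.b judges the same interaction against OR 1

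*Combined protocol and SAP*

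**What the plan says.** Final SAP 9 opens with "Trial stopping rules were approved by the Data Safety and Monitoring Board for the following events". Under 9.b it continues: "Unjust inducement will be defined as a statistically significant interaction between (a) incentive size and annual household income", or with economic well-being. Such an interaction, in the direction that poorer patients respond more to larger payments, "will be considered grounds for terminating the trial or suspending a trial arm". No margin is given, so the reference value is OR 1. Final Protocol 11.c uses the same kind of criterion for undue inducement: "A statistically significant interaction, in the direction that risk perception is less strongly associated with enrollment in higher-payment arms".

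Final SAP 5.c sets the final null hypothesis as inducement being present. It allows the investigators to "conclude the absence of undue or unjust inducement" when the interaction is small, meaning that an OR above 2.0 is excluded at one-sided 0.05. SAP 7.b uses one-sided 0.0427 for the same test.

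SAP 10 separates the looks: "In contrast to the final analyses, which will be structured as tests of non-inferiority, the interim analyses will be conducted as superiority tests". For the interim tests it adds: "We will use 1-sided significance levels of 0.0055, and 0.0219".

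The SAP does not say how a final interval wholly above 1 and wholly below 2.0 will be described. It also gives no unit for the OR to which 2.0 applies.

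**The concern.** Two reference values are attached to one construct. During the trial, a significant departure from OR 1 in the harmful direction counts as inducement and is grounds to stop. At the end, the same departure is reported as absence of inducement provided it is demonstrably smaller than OR 2.0.

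Aim I, the primary aim, asks whether the ethical concerns manifest, and the SAP hopes the findings will inform research regulation. Excluding an OR above 2.0 supports the statement that an interaction larger than 2.0 has been ruled out. It does not support the statement that inducement is absent, least of all when the interval lies entirely on the harmful side of 1.

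**Working it through.** **The plan's own figure first.** SAP 7.b states at least 80% power to exclude OR 2.0 with a true OR of 1, 96 patients per cell, 50% enrollment and one-sided 0.0427. Power = Φ(ln 2/SE − z).
- $0-arm OR fixed at 1, as 7.b describes: SE = √(4/48) = 0.289, power 75.2% (77.5% at 0.05).
- Sampling error in the $0 arm counted: SE = √(8/48) = 0.408, power 49.1% (52.1% at 0.05).

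The stated 80% is not reproduced. The point here does not depend on it, but these are the standard errors of the sizing contrast.

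**When can both criteria hold for one final estimate?** The lower bound exceeds 1 if ln OR > z·SE. The upper bound is below 2.0 if ln OR < ln 2 − z·SE. Both need SE < ln 2/(2z):
- one-sided 0.05 (z = 1.645): SE < 0.693/3.290 = 0.211
- one-sided 0.0427 (z = 1.720): SE < 0.693/3.440 = 0.2015

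The SAP gives no final superiority alpha. The lower bound is taken here at the same one-sided level as the final test.

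**Standard errors on other scales** (N = 576, 50% enrollment, information 0.25 per patient). Incentive scored 0/1/2 in equal arms has variance 2/3.
- Modifier per SD, incentive per level: √(1/(576 × 0.25 × 2/3)) = 0.102
- Modifier split evenly in two (variance 0.25), incentive per level: √(1/(576 × 0.25 × 2/3 × 0.25)) = 0.204
- Modifier per SD, high v low arm: √(2/(192 × 0.25)) = 0.204

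The units are assumptions, because the SAP states none.

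| Scale | SE | Lower bound > 1 if OR exceeds | 2.0 excluded if OR is below | Both hold |
|---|---|---|---|---|
| Sizing contrast, $0 OR fixed | 0.289 | 1.61 (1.64) | 1.24 (1.22) | never |
| Sizing contrast, four cells | 0.408 | 1.96 (2.02) | 1.02 (0.99) | never |
| Binary modifier, 0/1/2; or high v low per SD | 0.204 | 1.40 (1.42) | 1.43 (1.41) | 1.40-1.43 (never) |
| Per SD, per level | 0.102 | 1.18 (1.19) | 1.69 (1.68) | 1.18-1.69 (1.19-1.68) |

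Figures are at one-sided 0.05, with 0.0427 in brackets.

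**How often, on the last row.** At a true OR of 1.4 and alpha 0.05, the normal approximation gives Φ((ln 1.691 − ln 1.4)/0.102) − Φ((ln 1.183 − ln 1.4)/0.102) = Φ(1.85) − Φ(−1.65) ≈ 0.92. Simulated logistic models, whose standard error is slightly larger away from the null, give about 87% at 0.05 and, at a true OR of 1.41, 85% at 0.0427. The range is therefore about 85-92%. At 0.0427 the simulated share is 52% at a true OR of 1.2 and 4% at 1.0.

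**Would these results have crossed an interim boundary?** On the same scale:
- 50% of data: SE = 0.102/√0.5 = 0.144; one-sided 0.0055 needs OR > exp(2.543 × 0.144) = 1.44.
- 75% of data: SE = 0.102/√0.75 = 0.118; one-sided 0.0219 needs OR > exp(2.016 × 0.118) = 1.27.

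Estimates of 1.18 to 1.27 would cross neither.

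**The case against.** The strongest reply is that SAP 10 already separates the criteria. Section 9.b sits under the stopping rules, its consequence is stopping or suspending an arm, and there is no final superiority test. A reader might infer that the SAP gives one final result two contradictory labels. The documents do not support that, and this part of the reply stands. Separating the tests by time does not, however, change what 5.c says about an interval of 1.1 to 1.7.

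A reader might also infer that 9.b is the SAP's only definition of inducement. It is not: 7.b represents undue inducement by an interaction OR of 2.0 or greater, and 5.c judges smallness against that margin.

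The size can also be challenged, with reason. Only risk is said to be analysed as continuous (7.b). Table 1 lists income and economic well-being, the two modifiers in 9.b, as categorical. The wide window therefore applies to risk under assumed units and cannot be carried over to the unjust-inducement terms.

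Finally, any non-inferiority test permits an interval between the null value and the margin. That is true, and it is harmless when the conclusion is worded as exclusion of the margin. Here the wording is absence.

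**Conclusion.** The concern holds as a defect in how the final conclusion is worded, not as a formal contradiction at the final analysis. As written, 5.c would report absence of undue or unjust inducement when the whole interval lies between 1 and 2.0.

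Its reach depends on a unit the SAP does not give. It is impossible on the sizing contrast. It is a sliver at 0.05, and nothing at 0.0427, for a binary modifier with 0/1/2 incentive or for high v low per SD. It is wide (about 1.18 to 1.69) for risk per SD and incentive per level. The 85-92% figure belongs to that last scale with a true OR of 1.4 and is not a general rate.

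A reader might infer that every such result would have been grounds to stop earlier. That is not so: on the same assumptions the interim boundaries are about 1.44 and 1.27. Final Protocol 11.c also ties the DSMB's power to stop to a lower confidence bound above 2.0, which an interval of 1.1 to 1.7 cannot meet.

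The change should be made, because it governs what may be concluded on the primary aim.

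**What to change.** 1. In SAP 5.c, replace the conclusion of absence with the statement that an interaction OR above 2.0 is excluded.
2. Add to 5.c: if the upper bound is below 2.0 and the matching lower bound (same one-sided alpha as the final test) exceeds 1, report an interaction that is present but smaller than OR 2.0. If the upper bound is 2.0 or more, report that an OR above 2.0 is not excluded. Settle first whether the final alpha is 0.05 (5.c) or 0.0427 (7.b).
3. In SAP 9.b, state that the definition by statistical significance applies to interim monitoring only.
4. For each of risk, income and economic well-being, state the unit and direction of the OR to which 2.0 applies, including the incentive scores. Direction matters: if income is coded upward, the harmful interaction lies below 1.
5. Reconcile the interim criterion in SAP 9-10 (significance against no interaction) with the lower-bound-above-2.0 wording in Final Protocol 11.c.

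The cost is a few sentences. The lower bound comes from the model already fitted for the final test, so no further analysis or data are needed.
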